## 10.4. Appendix 4: Study Phases

### 10.4.1. Study Phases

Study phases for assessments scheduled at a set time will be defined according to the planned relative time of the assessment.

Any events/assessments for participants not in the ITT population will be assigned a Pre-treatment phase.

For all events and assessments, the study phases will be defined as follows:

Study Phase	Definition
Screening/Run-In period	Visit 1 date ≤ Assessment Date/Time < Date of randomization or randomized treatment start date, whichever is later.
On-Treatment during the Study	Randomized Treatment Start Date ≤ Event Onset Date or Assessment Date/Time ≤ Study Treatment Stop Date +1 day or any assessment with a missing or partial date unless there is evidence it was not on-treatment
Post-Treatment during the Study*	Randomized Treatment Stop Date +1 < Event Onset Date or Assessment Date/Time ≤ Last Scheduled Clinic Visit (i.e., Visit 5 (EOS Visit) or Early Withdrawal [EW] Visit) Note: if any participant does not receive a dose of randomized treatment then all post baseline data prior to early withdrawal or EOS visit is considered as post-treatment.
Post-Study	Event Onset Date > Last Scheduled Clinic Visit (i.e., Visit 5 (EOS Visit) or Early Withdrawal Visit) +1 day Note, for participants who continue in the study after IP discontinuation (i.e. where treatment discontinuation date < Visit 5 (EOS visit) date or EW visit date), the rule will be: Event Onset Date > Last Scheduled Clinic Visit (i.e. Visit 5 (EOS Visit) or EW Visit)

\*Only applicable for participants who continue in the study after IP discontinuation

Classification of a concomitant medication into study phases (pre-study period [at study entry], screening/run-in period, on-treatment during the study, post-treatment during the study, or post-study) will be made with reference to the study phase as defined above. A medication will be classified into every period in which it was taken. For medications with partial start and stop dates, the medication will be classified into every period in which it could have been taken.

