#### 10.7.2.1. Handling of Missing and Partial Dates

Element	Reporting Detail
General	
 
Partial dates will be displayed as captured in participant listing displays.
 
Dates which are completely missing will not be imputed, with the exception of the treatment stop date. Details for imputation of the treatment stop date are provided below.
 

Study treatment start and stop date	
 
If the study treatment start date is missing, the Visit 2 (Day 1) date will be used.
 
If overall treatment stop date is missing, it will be imputed as follows: 
 
For participants who attended an Early Withdrawal visit, use the date of the Early Withdrawal visit
 
For participants who attended the last on-treatment visit, use the Visit 5 (End of Study) date
 
For participants who died and did not attend the last on-treatment visit, use the date of death
 
For all other participants, use the last recorded exposure stop date
 
 
 
These rules will apply to both randomized double-blind treatment and open label FF100mcg for the treatment period.
 

Adverse Events	
 
The eCRF allows for the possibility of partial dates (i.e., only month and year) to be recorded for AE start and end dates; that is, the day of the month may be missing. In such a case, the following conventions will be applied for calculating the time to onset and the duration of the event: 
 
Missing Start Day: First of the month will be used unless this is before the start date of study treatment; in this case the study treatment start date will be used and hence the event is considered On-treatment as per Appendix 4: Study Phases
 
Missing Stop Day: Last day of the month will be used.
 
 
 
Completely missing start or end dates will remain missing, with no imputation applied. Consequently, time to onset and duration of such events will be missing.
 

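### The missing-start-day rule for adverse events has no same-month limit, so events recorded in a month wholly before first dose are counted as on-treatment

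*SAP*

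**What the plan says.** SAP Section 10.7.2.1 starts from what is collected: "The eCRF allows for the possibility of partial dates (i.e., only month and year) to be recorded for AE start and end dates". If the start day is missing, the first of the month is used "unless this is before the start date of study treatment; in this case the study treatment start date will be used". The same sentence states the consequence for the study phase, "hence the event is considered On-treatment", and cites Appendix 4. A missing stop day becomes the last day of the month.

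Study treatment here means randomized treatment and not the run-in inhaled steroid, because the section also says: "If the study treatment start date is missing, the Visit 2 (Day 1) date will be used".

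Appendix 4 (Section 10.4.1) defines on-treatment in two ways. The first clause is by date: "Randomized Treatment Start Date ≤ Event Onset Date or Assessment Date/Time ≤ Study Treatment Stop Date +1 day". The second is a default for incomplete dates: "any assessment with a missing or partial date unless there is evidence it was not on-treatment". Its Screening/Run-In phase begins at the Visit 1 date.

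Section 8 requires run-in, on-treatment and post-treatment AEs to be summarized separately.

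**The concern.** The rule is an ordinary cautious convention when the recorded month is the month of treatment start, because the true phase then cannot be told from month and year. It goes wrong when the recorded month is earlier. The first of that month is also before treatment start, so the reset fires even though the record shows that the event began before first dose.

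Three things follow:

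- No run-in AE with a missing start day can remain in the run-in summary (Table 3.4). All of them pass to the on-treatment AE, serious AE and special-interest tables, and to the versions per thousand person-years.
- The derived onset is first dose, and the derived stop can fall before it.
- Sections 10.7.2.1 and 10.4.1 give different answers for the same record, so two programmers could produce different tables.

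**Working it through.** The SAP states no figure to reproduce. The check applies the rule as written and then counts how often the recorded month would contradict it.

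**Inputs.** The run-in is 14 days, with Visit 1 at Day -14 and first dose at Day 1 (Sections 2.3 and 10.2.1). AEs are reviewed from Visit 1, and serious AEs from pre-screen, as early as Day -42 (Section 10.2.1).

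**Illustrative case: first dose 8 April 2018, so Visit 1 on 25 March 2018.**

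| Recorded onset | First of month before 8 April? | Onset under the rule | Phase under the rule | What the record shows |
|---|---|---|---|---|
| March 2018 | Yes | 8 April | On-treatment | Began before first dose |
| April 2018 | Yes | 8 April | On-treatment | Phase unknown |
| May 2018 | No | 1 May | On-treatment | Began after first dose (taking the participant as still on treatment) |

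If the March event stopped on 30 March, duration as stop minus start plus 1 is 30 March - 8 April + 1 = -8 days. That formula is an assumption for AEs; it is the one Section 10.6.3 gives for exacerbations. If the stop day is also missing, the stop becomes 31 March and the duration is -7 days.

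**Share of run-in days in an earlier month.** Assume first-dose dates uniform over the calendar and onset uniform over the run-in. For first dose on day d of a month, the preceding 14 days include d - 1 days of the same month. The other 15 - d lie in the previous month, for d = 1 to 14.

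- Sum over d = 1 to 14 of (15 - d) = 105 days per calendar month.
- Mean month length = 365/12 = 30.42 days.
- Share of run-in days in the previous month = 105 / (14 × 30.42) = 24.7%.
- Share of start dates with at least one such day = 14 / 30.42 = 46.0%.

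A day-by-day count over all start dates from 2017 to 2020 gives 24.6% and 46.0%.

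**Literal rule against a same-month limit, start day missing.**

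| Span before first dose | On-treatment, literal rule | On-treatment, same month and year only |
|---|---|---|
| 14 days (run-in) | 100% | 75.4% |
| 42 days (longest span for serious AEs) | 100% | 35.1% |

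The gap in each row is the part that the recorded month alone shows to be pre-treatment. A known end date before first dose would identify further cases within the same month.

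**Why the first of the recorded month is not enough as a repair.** A 14-day run-in reaches into the previous month only if first dose is on day 1 to 14. Visit 1 is then on day L + d - 14 of that previous month, where L is its length. The smallest value is 28 + 1 - 14 = 15. The first of the month therefore always precedes Visit 1, and the event would fall outside Screening/Run-In as Section 10.4.1 defines it.

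**The case against.** The best defence is that Section 10.7.2.1 offers its conventions for calculating time to onset and duration, while Section 8.2 sends phase assignment to Section 10.4.1. That section covers events as well as assessments and keeps an exception for evidence against on-treatment status. A recorded month wholly before first dose is such evidence. Since 10.7.2.1 cites Appendix 4, its sentence could be read as subject to that exception.

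This reading is possible but does not remove the fault. Section 10.7.2.1 declares the phase itself. Once it has replaced the onset with the first-dose date, the event meets the date clause of 10.4.1 directly and the exception is never reached. The exception is also worded for an assessment. Even on the favourable reading, the false onset and negative duration remain.

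Other parts of the defence stand:

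- The 25% is a share of AEs with a missing start day, not of all run-in AEs. The run-in is two weeks between two visits, both with AE review, so few start days should be missing.
- No formal comparison of AEs is planned. The modelled safety endpoints are vital signs and ECG intervals (Section 8.6.4).
- No listed summary table is titled for AE duration or time to onset, and listings show partial dates as captured, so the recorded month stays visible.

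A reader might infer that the rule biases the safety comparison toward or against UMEC. The SAP does not support that. The rule is identical in every arm and, under randomization, pre-treatment events are expected equally in each. Adding the same expected amount c to two incidences p and q leaves p - q essentially unchanged and moves (p + c)/(q + c) toward 1.

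**Conclusion.** The rule is wrong as written. It tests only whether the first of the recorded month precedes treatment start, so it classes as on-treatment some events that their own record shows to be earlier, and it conflicts with the exception in Section 10.4.1.

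About 25% of run-in AEs with a missing start day would be demonstrably misclassified, assuming uniform start and onset dates and a 14-day run-in. For serious AEs the share rises to about 65% (100% - 35.1%) if onsets are spread evenly over the full 42 days before first dose. The SAP does not say how many AEs lack a start day, so no effect on any reported rate can be stated.

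On-treatment counts and rates are inflated, since exposure in the denominator does not change, and the run-in table is depleted. Ratios are pulled toward 1, with no directional bias between arms. Efficacy is untouched. The point deserves correction because it is a stated rule with a wrong result and a cheap remedy, not because it threatens the trial's conclusions.

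**What to change.** Reconcile Section 10.7.2.1 with Section 10.4.1. For an AE with a missing start day whose first of the month precedes treatment start:

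1. Use the treatment start date, and class the event as on-treatment, only if the recorded month and year equal those of treatment start and the AE end date, if known, is not before treatment start.
2. Otherwise the onset is shown to be before treatment start, and the event is not on-treatment. If the recorded month is not before the Visit 1 month and any known end date is not before Visit 1, impute the later of the first of the recorded month and the Visit 1 date. The event then falls in Screening/Run-In as 10.4.1 defines it.
3. Keep onsets from before Visit 1, shown by the recorded month or a known end date, as pre-treatment. State where they are reported, because 10.4.1 defines no event phase before Visit 1 for ITT participants.

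In the illustrative case, the March event gets an onset of 25 March, a phase of Screening/Run-In and a duration of 30 - 25 + 1 = 6 days.

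The cost is one SAP sentence and a small change to the AE date derivation. No new data are needed.

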## 10.8. Appendix 8: Abbreviations & Trade Marks

### 10.8.1. Abbreviations

Abbreviation	Description
ADaM	Analysis Data Model
AE	Adverse Event
AIC	Akaike's Information Criteria
A&R	Analysis and Reporting
CDISC	Clinical Data Interchange Standards Consortium
CI	Confidence Interval
CPMS	Clinical Pharmacology Modelling & Simulation
CS	Clinical Statistics
CSR	Clinical Study Report
CTR	Clinical Trial Register
DBF	Database Freeze
DBR	Database Release
DOB	Date of Birth
DP	Decimal Places
eCRF	Electronic Case Record Form
EMA	European Medicines Agency
FDA	Food and Drug Administration
FDAAA	Food and Drug Administration Clinical Results Disclosure Requirements
GSK	GlaxoSmithKline
IA	Interim Analysis
ICH	International Conference on Harmonization
IDSL	Integrated Data Standards Library
IP	Investigational Product
ITT	Intent-To-Treat
MMRM	Mixed Model Repeated Measures
PCI	Potential Clinical Importance
PDMP	Protocol Deviation Management Plan
PP	Per Protocol
QC	Quality Control
QTcF	Frederica's QT Interval Corrected for Heart Rate
QTcB	Bazett's QT Interval Corrected for Heart Rate
RAP	Reporting & Analysis Plan
RAMOS	Randomization & Medication Ordering System
SAC	Statistical Analysis Complete
SDTM	Study Data Tabulation Model
SOP	Standard Operation Procedure
TA	Therapeutic Area
TFL	Tables, Figures & Listings

**10.8.2. Trademarks**

Trademarks of the GlaxoSmithKline Group of Companies	Trademarks not owned by the GlaxoSmithKline Group of Companies
ELLIPTA	SAS

## 10.9. Appendix 9: List of Data Displays

### 10.9.1. Data Display Numbering

The following numbering will be applied for RAP generated displays:

Section	Tables	Figures
Study Population	1.1 to 1.n	1.1 to 1.n
Efficacy	2.1 to 2.n	2.1 to 2.n
Safety	3.1 to 3.n	3.1 to 3.n
Section	Listings	
ICH Listings	1 to x	
Other Listings	y to z	

### 10.9.2. Mock Example Shell Referencing

Displays will follow IDSL standards where possible. Example mock-up displays will be provided in separate documents and stored in the eTMF. Modifications and additional specifications for IDSL outputs will also be detailed in these documents, therefore where the mock displays differ from IDSL, the mock display should be followed.

### 10.9.3. Deliverables

Delivery	Description
SAC	Final Statistical Analysis Complete

#### 10.9.4. Study Population Tables

Study Population Tables					
No.	Population	IDSL / Example Shell	Title	Programming Notes	Deliverable
Subject Disposition					
1.1.	ITT	ES1	Summary of Subject Disposition	ICH E3, FDAAA, EudraCT	SAC
1.2.	ITT	SD1	Summary of Treatment Status	ICH E3	SAC
1.3.	ITT	Study Specific	Summary of Treatment Status at Each Clinic Visit		SAC
1.4.	All Subjects Enrolled	ES6	Summary and Reason for Screen Failures and Run-in Failures	Journal Requirements	SAC
1.5.	All Subjects Enrolled	Study Specific	Summary of Rescreens in the Study and Failure Reasons		SAC
1.6.	All Subjects Enrolled	NS1	Summary of Subject Enrolment by Country and Site ID	EudraCT/Clinical Operations	SAC
1.7.	ITT	NS1	Summary of Subjects Included in the ITT Population by Country and Site ID		SAC
Protocol Deviation					
1.8.	ITT	IE2	Summary of Inclusion, Exclusion, or Randomization Criteria Deviations		SAC
1.9.	ITT	DV1	Summary of Important Protocol Deviations	ICH E3	SAC
Population Analyzed					
1.10.	All Subjects Enrolled	SP1	Summary of Study Populations	IDSL	SAC
Demographic and Baseline Characteristics					
1.11.	ITT	DM1	Summary of Demographic Characteristics	ICH E3, FDAAA, EudraCT	SAC
1.12.	ITT	DM1	Summary of Demographic Characteristics by Country		SAC

Study Population Tables					
No.	Population	IDSL / Example Shell	Title	Programming Notes	Deliverable
1.13.	All Subjects Enrolled	DM11	Summary of Age Ranges	EudraCT	SAC
1.14.	ITT	DM5	Summary of Race and Racial Combinations	ICH E3, FDA, FDAAA, EudraCT	SAC
1.15.	ITT	DM6	Summary of Race and Racial Combination Details		SAC
1.16.	ITT	Study Specific	Summary of Disease Duration		SAC
1.17.	ITT	Study Specific	Summary of Asthma Medical History Questionnaire		SAC
1.18.	ITT	Study Specific	Summary of Exacerbation History		SAC
1.19.	ITT	SU1 (subset)	Summary of Smoking Status		SAC
1.20.	ITT	Study Specific	Summary of Cardiovascular History / Risk Factors		SAC
1.21.	ITT	FH1	Summary of Family History of Cardiovascular Risk Factors		SAC
1.22.	ITT	Study Specific	Summary of Pneumonia History		SAC
1.23.	ITT	Study Specific	Summary of Clinic Spirometry at Screening and Randomization		SAC
1.24.	ITT	Study Specific	Summary of Change in Clinic Pre-Bronchodilator / Pre-Dose FEV1 (L) during the Run-in Period		SAC
1.25.	ITT	Study Specific	Summary of Home Spirometry During the Run-in Period		SAC
1.26.	ITT	Study Specific	Summary of ACQ score at Screening and Randomization		SAC
1.27.	ITT	Study Specific	Summary of Change from Screening in ACQ-6 Score during the Run-in Period		SAC
1.28.	ITT	MH4	Summary of Current Medical Conditions	ICH E3	SAC
1.29.	ITT	MH4	Summary of Past Medical Conditions	ICH E3	SAC
Prior and Concomitant Medications					
1.30.	ITT	Study Specific	Summary of Asthma Maintenance Therapy at Study Entry		SAC

Study Population Tables					
No.	Population	IDSL / Example Shell	Title	Programming Notes	Deliverable
1.31.	ITT	Study Specific	Summary of Asthma Maintenance Therapy Following Treatment Discontinuation		SAC
1.32.	ITT	CM1	Summary of Asthma Concomitant Medications at Study Entry	ICH E3	SAC
1.33.	ITT	CM1	Summary of Asthma Concomitant Medications During the Screening/Run-in Period		SAC
1.34.	ITT	CM1	Summary of On-Treatment Asthma Concomitant Medications		SAC
1.35.	ITT	CM1	Summary of Post-Treatment Asthma Medications		SAC
1.36.	ITT	CM1	Summary of Post-Study Asthma Medications		SAC
1.37.	ITT	CM1	Summary of On-Treatment Non-Asthma Concomitant Medications		SAC
1.38.	ITT	CM1	Summary of Post-Treatment Non-Asthma Medications		SAC
1.39.	ITT	CM1	Summary of Post-Study Non-Asthma Medications		SAC
Treatment Compliance					
1.40.	ITT	TC1	Summary of Treatment Compliance (%)		SAC

### 10.9.5. Study Population Figures

Study Population Figures					
No.	Population	IDSL / TST ID / Example Shell	Title	Programming Notes	Deliverable [Priority]
Subject Disposition					
1.1.	ITT	TTE10	Kaplan-Meier Plot of Time to Early Discontinuation from Study Treatment		SAC
1.2.	ITT	TTE10	Kaplan-Meier Plot of Time to Early Withdrawal from the Study		SAC

### 10.9.6. Efficacy Tables

Efficacy: Tables					
No.	Population	IDSL / Example Shell	Title	Programming Notes	Deliverable
Primary Efficacy Endpoint: Trough FEV1					
2.1.	ITT	Study Specific	Summary of Baseline Clinic Trough FEV 1 (L)		SAC
2.2.	ITT	Study Specific	Summary of Clinic Trough FEV 1 (L) (On- and Post-Treatment)	On- and post-treatment data	SAC
2.3.	ITT	Study Specific	Analysis of Mean Change from Baseline in Clinic Trough FEV 1 (L) (On- and Post-Treatment)	On- and post-treatment data	SAC
2.4.	ITT	Study Specific	Summary of Clinic Trough FEV 1 (L) by Treatment Status (On- and Post-Treatment)	On- and post-treatment data (separately)	SAC
2.5.	ITT	Study Specific	Sensitivity Analysis of Mean Change from Baseline in Clinic Trough FEV 1 (L) (Jump to Reference) (On- and Post-Treatment)	On- and post-treatment data. Multiple imputation using jump to reference.	SAC
2.6.	ITT	Study Specific	Sensitivity Analysis of Mean Change from Baseline in Clinic Trough FEV 1 (L) (Tipping Point) UMEC 62.5mcg vs Placebo (On- and Post-Treatment)	On- and post-treatment data. Tipping point analysis	SAC
2.7.	ITT	Study Specific	Sensitivity Analysis of Mean Change from Baseline in Clinic Trough FEV 1 (L) (Tipping Point p-value Grid) UMEC 62.5mcg vs Placebo (On- and Post-Treatment)	On- and post-treatment data. Tipping point analysis	SAC
2.8.	ITT	Study Specific	Sensitivity Analysis of Mean Change from Baseline in Clinic Trough FEV 1 (L) (Tipping Point) UMEC 31.25mcg vs Placebo (On- and Post-Treatment)	On- and post-treatment data. Tipping point analysis	SAC
2.9.	ITT	Study Specific	Sensitivity Analysis of Mean Change from Baseline in Clinic Trough FEV 1 (L) (Tipping Point p-value Grid) UMEC 31.25mcg vs Placebo (On- and Post-Treatment)	On- and post-treatment data. Tipping point analysis	SAC
2.10.	ITT	Study Specific	Analysis of Mean Change from Baseline in Clinic Trough FEV 1 (L) (on-Treatment)	On-treatment data only	SAC

Efficacy: Tables					
No.	Population	IDSL / Example Shell	Title	Programming Notes	Deliverable
2.11.	ITT	Study Specific	Analysis of Mean Change from Baseline in Clinic Trough FEV 1 (L) excluding sites with data concerns (On- and Post-Treatment)	On- and post-treatment data	SAC
2.12.	ITT	Study Specific	Summary of Clinic Trough FEV 1 (L) by Gender (On- and Post-Treatment)	On- and post-treatment data	SAC
2.13.	ITT	Study Specific	Summary of Clinic Trough FEV 1 (L) by Age (On- and Post-Treatment)	On- and post-treatment data	SAC
2.14.	ITT	Study Specific	Summary of Clinic Trough FEV 1 (L) by Race (On- and Post-Treatment)	On- and post-treatment data	SAC
2.15.	ITT	Study Specific	Summary of Clinic Trough FEV 1 (L) by Region (On- and Post-Treatment)	On- and post-treatment data	SAC
2.16.	ITT	Study Specific	Summary of Clinic Trough FEV 1 (L) by Eosinophils at Screening (On- and Post-Treatment)	On- and post-treatment data	SAC
2.17.	ITT	Study Specific	Significance Levels for All Covariates Included in the Analysis Model for Change from Baseline in Trough FEV 1 (L) and Interactions with Treatment (On- and Post-Treatment)	On- and post-treatment data	SAC
Secondary Efficacy Endpoint: FEV1 at 3 hours post Dose					
2.18.	ITT	Study Specific	Summary of Change from Baseline in Clinic FEV 1 at 3 Hours Post Dose (On-Treatment)	On-treatment data only	SAC
2.19.	ITT	Study Specific	Analysis of Mean Change from Baseline in Clinic FEV 1 at 3 Hours Post Dose at Week 24 (On-Treatment)	On-treatment data only	SAC
Exploratory Efficacy Endpoints					
2.20.	ITT	Study Specific	Summary of Clinic Spirometry Data (On- and Post-Treatment)	On- and post-treatment data	SAC
2.21.	ITT	Study Specific	Summary of Home AM PEF (L/min) (On- and Post-Treatment)	On- and post-treatment data	SAC
2.22.	ITT	Study Specific	Analysis of Mean Change from Baseline in Home AM PEF (L/min) over the 24 Week Treatment Period by 4-Weekly Intervals (On- and Post-Treatment)	On- and post-treatment data	SAC

Efficacy: Tables					
No.	Population	IDS / Example Shell	Title	Programming Notes	Deliverable
2.23.	ITT	Study Specific	Summary of Home PM PEF (L/min) (On- and Post-Treatment)	On- and post-treatment data	SAC
2.24.	ITT	Study Specific	Analysis of Mean Change from Baseline in Home PM PEF (L/min) over the 24-Week Treatment Period by 4-Weekly Intervals (On- and Post-Treatment)	On- and post-treatment data	SAC
2.25.	ITT	Study Specific	Summary of Home Trough FEV 1 (L) (On- and Post-Treatment)	On- and post-treatment data	SAC
2.26.	ITT	Study Specific	Analysis of Mean Change from Baseline in Home Trough FEV 1 (L) over the 24-week Treatment Period by 4-Weekly Intervals (On- and Post-Treatment)	On- and post-treatment data	SAC
2.27.	ITT	Study Specific	Analysis of Mean Change from Baseline in Home Trough FEV 1 (L) up to Week 8 by 1-Week Intervals (On- and Post-Treatment)	On- and post-treatment data	SAC
2.28.	ITT	Study Specific	Summary of Home PM FEV 1 (L) (On- and Post-Treatment)	On- and post-treatment data	SAC
2.29.	ITT	Study Specific	Analysis of Mean Change from Baseline in Home PM FEV 1 (L) over the 24-week Treatment Period by 4-Weekly Intervals (On- and Post-Treatment)	On- and post-treatment data	SAC
2.30.	ITT	Study Specific	Summary of Baseline Daily Rescue Medication use (Puffs/Day)		SAC
2.31.	ITT	Study Specific	Summary of Daily Rescue Medication Use (Puffs/Day) (On- and Post-Treatment)	On- and post-treatment data	SAC
2.32.	ITT	Study Specific	Analysis of Mean Change from Baseline in Daily Rescue Medication use (Puffs/Day) over the 24-week Treatment Period by 4-Weekly Intervals (On- and Post-Treatment)	On- and post-treatment data	SAC
2.33.	ITT	Study Specific	Summary of Baseline SGRQ Total Score		SAC
2.34.	ITT	Study Specific	Summary of SGRQ Total Score (On- and Post-Treatment)	On- and post-treatment data	SAC
2.35.	ITT	Study Specific	Analysis of Mean Change from Baseline in SGRQ Total Score (On- and Post-Treatment)	On- and post-treatment data	SAC

Efficacy: Tables					
No.	Population	IDS / Example Shell	Title	Programming Notes	Deliverable
2.36.	ITT	Study Specific	Summary and Analysis of Percent of Patients Meeting a Responder Threshold of $\geq 4$ Points Improvement (Decrease) from Baseline for the SGRQ Total Score (On- and Post-Treatment)	On- and post-treatment data	SAC
2.37.	ITT	Study Specific	Summary of Baseline SGRQ Domain Scores		SAC
2.38.	ITT	Study Specific	Summary of SGRQ Domain Scores (On- and Post-Treatment)	On- and post-treatment data	SAC
2.39.	ITT	Study Specific	Analysis of Mean Change from Baseline in SGRQ Domain Scores (On- and Post-Treatment)	On- and post-treatment data	SAC
2.40.	ITT	Study Specific	Summary of Baseline AQLQ Total Score		SAC
2.41.	ITT	Study Specific	Summary of AQLQ Total Score (On- and Post-Treatment)	On- and post-treatment data	SAC
2.42.	ITT	Study Specific	Analysis of Mean Change from Baseline in AQLQ Total Score (On- and Post-Treatment)	On- and post-treatment data	SAC
2.43.	ITT	Study Specific	Summary and Analysis of Percent of Patients Meeting a Responder Threshold of $\geq 0.5$ Points Improvement (Increase) from Baseline for the AQLQ Total Score (On- and Post-Treatment)	On- and post-treatment data	SAC
2.44.	ITT	Study Specific	Summary of Baseline E-RS Total Score		SAC
2.45.	ITT	Study Specific	Summary of E-RS Total Score (On- and Post-Treatment)	On- and post-treatment data	SAC
2.46.	ITT	Study Specific	Analysis of Mean Change from Baseline in E-RS Total Score (On- and Post-Treatment) over the 24-week Treatment Period by 4-Weekly Intervals (On- and Post-Treatment)	On- and post-treatment data	SAC
2.47.	ITT	Study Specific	Summary of ACQ-5 Total Score (On- and Post-Treatment)	On- and post-treatment data	SAC
2.48.	ITT	Study Specific	Shift in ACQ-5 Control Category from Baseline to Week 24 (On- and Post-Treatment)	On- and post-treatment data	SAC

Efficacy: Tables					
No.	Population	IDSL / Example Shell	Title	Programming Notes	Deliverable
2.49.	ITT	Study Specific	Analysis of Mean Change from Baseline in ACQ-5 Total Score (On- and Post-Treatment)	On- and post-treatment data	SAC
2.50.	ITT	Study Specific	Summary and Analysis of Percent of Patients Meeting a Responder Threshold of $\geq 0.5$ in change (decrease) from baseline for the ACQ-5 (On- and Post-Treatment)	On- and post-treatment data	SAC
2.51.	ITT	Study Specific	Summary of Moderate and Severe Asthma Exacerbations (On- and Post-Treatment)	On- and post-treatment data	SAC
2.52.	ITT	Study Specific	Analysis of Moderate/Severe Asthma Exacerbations (On- and Post-Treatment)	On- and post-treatment data	SAC
2.53.	ITT	Study Specific	Summary and Analysis of Time to First Moderate/Severe Asthma Exacerbation (Days) (On- and Post-Treatment)	On- and post-treatment data	SAC
2.54.	ITT	Study Specific	Analysis of Severe Asthma Exacerbations (On- and Post-Treatment)	On- and post-treatment data	SAC
2.55.	ITT	Study Specific	Summary and Analysis of Time to First Severe Asthma Exacerbation (Days) (On- and Post-Treatment)	On- and post-treatment data	SAC
2.56.	ITT	Study Specific	Summary of Baseline Global Assessment of Severity		SAC
2.57.	ITT	Study Specific	Summary of Global Assessment of Severity and Response to Treatment (On- and Post-Treatment)	On- and post-treatment data	SAC

